#### 7.5 CRITERIA FOR PARTICIPANT DISCONTINUATION

Each participant will be informed of her and her partner's right to withdraw from the study at any time and for any reason. A participant may be discontinued from study treatment at any time if the participant, the Investigator, or the Sponsor feels that it is not in the participant's best interest to continue on study.

Participants who sign the informed consent and agree to participate in the study, but do not meet eligibility criteria will be considered screen failures.

Following enrollment, participants may be discontinued from the study for the following reasons:

- Failure to follow protocol requirements that is judged severe enough by the investigator to significantly affect study outcomes or requires discontinuation of study treatment
- Having an average of >5 progressively motile sperm per HPF in the cervical mucus 2-3 hours after intercourse using a Caya diaphragm with nonoxynol-9 if the result was clearly the result of the participant not using or inserting the diaphragm properly.
- Adverse event, including diagnosis of symptomatic bacterial vaginosis (BV) or an STI (in the
  participant or her partner), or any intercurrent illness that would jeopardize the participant's health
  or the interpretation of the results of the study. (An outbreak of genital herpes or condylomata
  would require discontinuation.)
- Pregnancy
- Loss to follow-up
- Participant withdrawal of consent
- Sponsor decision to discontinue trial

Prior to discontinuing a participant from the study, the site should contact Daré or designee. The reason for discontinuation must be recorded on the appropriate section of the participant's CRF.

Version: 06.00 (FINAL) Date: June 13, 2019

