#### 9.2.1 Baseline PCT Visits and Procedures:

- a) Visit 2 (BP1) Cervical Mucus Check (CMC) visit, on the day of the "high" result or the next
  - Entry criteria will be reviewed to confirm the participant's eligibility.
  - Diary entries will be reviewed. Particular attention will be paid to:
    - o Any new or worsening medical problems or symptoms or used any medications since the last study visit.
    - o Partner AEs involving the urogenital system and serious AEs.e
    - o Whether the participant used condoms until Day 10, and then refrained from intercourse and other vaginal activity, and whether her male partner refrained from ejaculation since Day 10. If instructions were not followed, she will be reinstructed. If she used a spermicide or spermicidal lubricated condom since day 10, Visit 2 (BP1) will be rescheduled in the next cycle. Otherwise, the visit may continue at the investigator's discretion.
  - A directed physical exam will be performed if indicated.
  - The participant will undergo a pelvic exam:
    - o Signs of irritation of the external genitalia, cervix, and vagina, as observed with the naked eye, will be noted.
    - o If the participant has symptoms of an infection at this visit, a urine dipstick and/or wet mount will be performed, as indicated. If a UTI or vaginal candidiasis is diagnosed, she will be treated with oral medication and Visit

<sup>e Product-related male AEs will be collected at visits during and after Ovaprene use.

f "Other vaginal activity" includes insertion of vaginal medications/products other than the study product (prescription or over-the-counter), as well as insertion of sex toys, fingers, or anything else into the vagina. Tampons may be used during all days of menses in the Baseline PCT and Caya PCT cycles, but only during the first three days of menses in Ovaprene cycles.

Version: 06.00 (FINAL) Date: June 13, 2019

2 (BP1) will be rescheduled in the next cycle. Other tests may be performed as indicated; if a test is positive for BV or an STI, the participant will be treated but not continued in the study.

- o Cervical mucus will be examined for pH, midcycle characteristics, and the presence of sperm (see **Appendix 2**).
- o Vaginal sample(s) will be collected for pH, the presence of sperm, and baseline levels of microflora, antibacterial activity, and soluble markersg.

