characteristics and sperm  Cervical mucus by pipette - ferrous		Х	Х		Х	Х							Х	Х			Х
gluconate									Х		Х	Х	Х	Х		Х	х
Replace Ovaprene if displaced									X		X		X	X		X	X
Vaginal lavage - antibacterial activity,											7.			,			
soluble markers		Χ	X 				$X^{11}$	Χ	Х	Х	Х	Х		X 		Х	Х
Remove Ovaprene - swab for staph																	
aureus and store											Χ					Χ	Χ
Colpo exam of cervix under																	
magnification	Х						Χ				Χ	Χ				Χ	Х
Pap Test 	Х									1							
GC/CT if using cervical specimens 	Χ																Χ
Colpo exam of fornices and of vagina																	
(latter while removing speculum)	Х						Х				Х	Х				Χ	Х
Ovaprene Fit Test				Χ													
Caya Fit Test	Х																Х
Insert Ovaprene 							Χ					Χ					Χ
Remove Caya						Χ											Χ
Dispense Caya					Χ												
Explain Trials.ai	Х																
Dispense OPK Kit	Χ			Χ				Χ				Х				Χ	Χ
Dispense condoms	Χ			Χ							0					0	Χ

<sup>1 Medical and Obstetrical history will include contraceptive and gynecological history also.

Version: 06.00 (FINAL) Date: June 13, 2019

<sup>2 A physical exam will be performed if the history is significant for a medical condition. The directed physical exam can be performed at any visit.

<sup>3 HIV testing will be performed on all female participants. HIV testing is available for the male partners, if requested.

<sup>4 Urinalysis is only required if participant is symptomatic for UTI. Treat UTI with oral meds. If Visit 1, continue participant. If after Visit 1, reschedule visit.

<sup>5 The pelvic exam at every visit should look for signs of irritation of the external genitalia, cervix and vagina, as seen with the naked eye. A Pap Test will be performed at Visit 1, if necessary, consistent with the standard medical practice as outlined in the study manual.

<sup>6 **STI**: treat with oral meds and do not continue participant.

<sup>7 **Candidiasis**: treat with oral meds. If Visit 1, continue participant. If after Visit 1, reschedule visit. **BV**: treat with oral meds. If diagnosed at Visit 1, continue participant. If diagnosed after Visit 1, do not continue participant.

<sup>8 EVMS only: Cervical mucus pH will also be tested at 0.5, 1, 2, 4, and 6 hour time points, if possible.

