#### 3.1.3 Analysis Conventions

This section details general policies used for the statistical analyses. Departures from these general policies may be given in the specific detailed sections of this statistical analysis plan. When this situation occurs, the rules set forth in the specific section take precedence over the general policies. The following policies will be applied to all data presentations and analyses.

- Discrete variables' summary statistics will consist of the number and percent of responses in each category
- Continuous variables' summary statistics will include the sample size (number of non-missing observations), mean, median, standard deviation (SD), minimum and maximum, abbreviated as "6-number summary statistics", where minimum and maximum may be replaced with 25th and 75th percentiles, i.e., interquartile range (IQR), if desired.
- All mean values will be formatted to one more decimal place than the measured value. Standard deviation values will be formatted to two more decimal places than the measured value. Median values will be formatted to same decimal place as the measured values when that is possible without losing accuracy; otherwise, they will be formatted to one more decimal place than the measured values.
- All percentages will be rounded to one decimal place. The number and percent of responses
  will be presented in the form XX (XX.X), where the percentage is in the parentheses. The
  decimal of the percentage may be dropped due to space constraints when creating a table.
  The denominator for percentage calculations will be the number of non-missing observations,
  or the analysis population's sample size if no such number of non-missing observations is
  presented along with the categorical values.
- All by-subject data listings will be sorted for presentation in order of site number, subject number, and date of procedure or event.
- When necessary for analysis purposes, partial dates will be completed (i.e., turned into complete dates) using the most conservative approach: for example, if a concomitant medication start date had Month and Year parts only, it's assumed to be the first day of that month; while if the stop date had Month and Year parts only, it's assumed to be the last day of that month.
- All analysis and summary tables will have the population sample size in the column heading.
- Calculating change from Baseline to a visit will be done as follows:

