#### 3.7.6 Nugent's Score and Vaginal Microflora

Nugent's score (from central lab, if available; otherwise, use local lab) and antibacterial (anti-E. coli) activity in CVF, soluble markers of inflammation in CVF and changes in these endpoints from Visit OS1 to OS2 through OS5 and from Visit OP1 to OP5, will be summarized by 6-number statistics at each visit. Antibacterial and soluble marker changes will also be summaries for these changes: BP1 to OS1, BP2 to OP3 and OP1 to OP3. Vaginal microflora and staphylococcus aureus assessment on the ring will not be analyzed by HD and the vendor analysis of the data will be included as an appendix of the final clinical study report.

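### By-visit Nugent summaries (SAP 3.7.6) leave out women already withdrawn for BV, so they lean towards no effect; a per-woman count over all Ovaprene users should be added

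*SAP*

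**What the plan says.** **Analysis.** SAP 3.7.6 plans Nugent score, with "changes in these endpoints from Visit OS1 to OS2 through OS5 and from Visit OP1 to OP5", and says that these "will be summarized by 6-number statistics at each visit". Under SAP 3.1.3 the summaries of a continuous variable "will include the sample size (number of non-missing observations), mean, median, standard deviation (SD), minimum and maximum", where the last two may be replaced by quartiles. No last-value, worst-value or imputation rule is given for Nugent, and one table is planned (14.3.5.8, Ovaprene population).

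**Withdrawal.** Protocol 9.2.1 (Visit 2) says that "if a test is positive for BV or an STI, the participant will be treated but not continued in the study", and later visits manage such tests as described for Visit 2. Appendix 1, footnote 7, says of BV: "If diagnosed after Visit 1, do not continue participant". Protocol 7.5 is worded differently. Among the reasons for which an enrolled woman may be discontinued, it lists "Adverse event, including diagnosis of symptomatic bacterial vaginosis (BV) or an STI".

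**Trigger for testing.** Protocol 9.2.1: "If the participant has symptoms of an infection at this visit, a urine dipstick and/or wet mount will be performed, as indicated". Appendix 1 marks the wet mount as done only if indicated after screening.

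**Nugent schedule.** Protocol Appendix 1 has Nugent at screening, OS1–OS5, OP1, OP5 and unscheduled visits, but not at OP2, OP3 or OP4. Nugent of 7 or more excludes a woman at entry (Protocol 8.2). No rule after enrollment withdraws a woman on Nugent score alone.

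**The concern.** Change in Nugent score is part of secondary safety endpoint 3e, and Protocol Table 14 states its purpose as assessing the device's effect over a cycle. A woman whose flora is disturbed enough to give a BV diagnosis leaves the study and supplies no further scores. Means and medians at later visits then come from women not diagnosed with BV. The PCT-cycle change starts afresh at OP1, so a woman withdrawn in the safety cycle is not in it at all.

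The missing values are therefore related to what the score measures, and they are missing in the direction that favours the device. The protocol's introduction expects the ring's acidic products not to disturb the vaginal flora materially. Late-visit averages from the women who remain are weak support for that expectation.

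**Working it through.** The plan contains no Nugent effect size, SD, BV rate or power figure to reproduce, because study size was set by feasibility (Protocol 14.1, SAP 2.5). The check is a trace of the rules, followed by an illustration on assumed inputs.

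**1. What happens to a woman diagnosed with BV, by visit of diagnosis**

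| Diagnosed at | Nugent score at that visit | Later safety-cycle rows | OP1-to-OP5 change |
|---|---|---|---|
| OS2–OS4 | Scheduled, counted | Absent | Absent from both PCT cycles |
| OS5 | Scheduled, counted | None remain | Absent from both PCT cycles |
| OP2–OP4 | Not scheduled; present only if an unscheduled sample is taken | Not applicable | Absent from that cycle (no OP5) and any later one |
| OP5, first PCT cycle | Scheduled, counted | Not applicable | Present for that cycle, absent from the second |

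The discontinuation procedures (Protocol 9.8) name no Nugent sample. SAP 3.7 lets an unscheduled repeat replace a scheduled value, but it does not fill later visits. Protocol 7.3 allows replacement of women who stop early, so a fall in the number at a visit is not a dependable sign of the loss.

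**2. Worked example (assumed)**

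Thirty women start. Three rise from Nugent 2 to 8 (+6), are sampled at OS3, diagnosed there and withdrawn. The others do not change.

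- OS3: n = 30, mean change = 3 × 6 / 30 = +0.6.
- OS4 and OS5: n = 27, mean change = 0.0.
- OP1 to OP5: none of the three contributes.
- Per-woman count: 3/30 = 10.0%, exact 95% CI 2.1% to 26.5%.

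The by-visit table would read as a small shift that resolves by OS4. The per-woman count keeps the three in view. With 1 to 6 such women, the shift not shown at OS5 is 1 × 6 / 30 = 0.2 to 6 × 6 / 30 = 1.2 points.

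**3. Range over assumptions**

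If *k* of *N* users are withdrawn after a rise of *d* and the rest have mean change 0, the mean in those remaining is 0, and the mean with the withdrawn women counted at their last score is *kd/N*.

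| N | k = 1, d = 3 | k = 3, d = 5 | k = 5, d = 7 |
|---|---|---|---|
| 25 | 3/25 = 0.12 | 15/25 = 0.60 | 35/25 = 1.40 |
| 35 | 3/35 = 0.09 | 15/35 = 0.43 | 35/35 = 1.00 |
| 45 | 3/45 = 0.07 | 15/45 = 0.33 | 35/45 = 0.78 |

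This measures what the late rows do not show. It does not estimate the score that a treated woman would have had at OS5.

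**4. Is at least one such withdrawal likely?**

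The chance is 1 − (1 − *p*)^25 for 25 users: 72% at an assumed BV risk of 5%, 93% at 10% and 99.6% at 20%.

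**The case against.** The case on the other side has several good parts.

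- *No rule withdraws a woman for her Nugent score.* This stands. Testing for BV after Visit 1 follows symptoms, while Nugent is taken from every woman at its scheduled visits. A woman with a high score and no diagnosis stays and is counted. A reader might infer that dropout is determined by the score itself; the documents support only the loss of diagnosed, mainly symptomatic, BV.
- *The same table can show the rise.* This stands in part. A score at the diagnosing visit counts there, and n and usually the maximum are shown. It fails for diagnosis at OP2–OP4 without an unscheduled sample, and it does not help the rows for later visits.
- *BV is already reported.* A reader might infer that BV is hidden from the study report. It is not. Disposition reasons (SAP 3.2), adverse events by preferred term and the listings of urogenital and discontinuing events (SAP 3.7.1) would show it, and Protocol 14.2.4 makes urogenital, product-related or serious events the primary evaluation of safety. None of these displays is linked to the Nugent table.
- *Restarting at OP1 is intended.* This stands. Protocol Table 14 defines that comparison as one cycle of use against before insertion. It answers its own question and is not a defect.
- *Nothing is tested.* This is true, since these comparisons are descriptive and no decision rule uses them. A descriptive table can still mislead a reader about the flora.

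**Conclusion.** The concern holds in a limited form. Summaries of Nugent change at visits after a BV diagnosis, and in later PCT cycles, leave out the women withdrawn for BV, so the endpoint 3e table leans towards no effect. The direction follows from the documents' rules if BV is accompanied by a raised Nugent score.

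The size does not follow from them. The shifts of about 0.1 to 1.4 points rest on assumed numbers of users, withdrawals and points of rise, with no change in everyone else. A reader might take any of these figures as the expected bias, but the documents give no BV rate to support that. If no woman is withdrawn for BV, this bias is absent.

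Protocol 7.5 (permissive, symptomatic BV) and Protocol 9.2.1 with Appendix 1 (not continued after a positive test or diagnosis) must be reconciled, since the wording determines who leaves. This point takes no view on which is right.

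**What to change.** Add to SAP 3.7.6, for all women treated with Ovaprene:

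1. The number and percent, with exact 95% CI, who have Nugent 7 or more at any post-insertion visit (scheduled or unscheduled) or are discontinued for BV, for each Ovaprene cycle and overall. The threshold is the protocol's own entry limit.
2. A footnote to the by-visit change table giving, at each visit, the number of values missing because of BV discontinuation.

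Keep the OP1-to-OP5 comparison and leave the clinical rules to the reconciliation noted above. A row with each woman's last post-insertion value is optional. It adds little in PCT cycles, where OP5 is the only scheduled post-insertion Nugent.

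A per-woman count matches what the SAP already plans elsewhere: number and percent worsened for colposcopy (3.7.4) and improved, unchanged or worsened for the gynecological examination (3.7.5).

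The cost is one descriptive table and one footnote from data already collected. Part of the table overlaps the adverse event tables; the Nugent count and its combination with BV discontinuation are new.

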#### 3.7.7 Physical Examination

Physical examination is optional, and will be performed if the history is significant for a medical condition. The number and percent of subjects in each category of "Normal" / "Abnormal" will be presented by body system at each visit.

#### 3.8 Acceptability Questionnaire

An acceptability questionnaire developed for this study is administered at the Ovaprene® cycles. The following questions' answers will be summarized with the number and percent of subjects in each response category at each visit, as well as shift tables (frequencies of each categorical response at one visit cross tabulate with the frequencies from another visit, from Visit OS5 to Visits OP3A and OP3B, and from Visit OP3A to Visit OP3B):

- 1. How would you describe the ease of Ovaprene® insertion? (Response: Very easy, Fairly easy, Neither easy nor difficult, Somewhat difficult, Very difficult)
- 2. During the study, were you aware of the Ovaprene® device during your normal daily activities? (Response: Always, Most of the time, Some of the time, Rarely, Never)
- 3. How did it feel to have the Ovaprene® device in place when you were not having sex? (Response: Usually comfortable, Neither comfortable nor uncomfortable, Sometimes comfortable and sometimes uncomfortable, Usually uncomfortable)
- 4. Have you had sex with the device in place? (Response: No, Yes)
- 5. How did it feel to have the Ovaprene® device in place when you were having sex? (Response: Usually comfortable, Neither comfortable nor uncomfortable, Sometimes comfortable and sometimes uncomfortable, Usually uncomfortable)
- 6. If Ovaprene® became available and you needed protection from pregnancy, would discomfort prevent you from using it? (Response: No, Yes)

- 7. Was your partner aware of the device when you were having sex? (Response: Always, Most of the time, Some of the time, Rarely, Never)
- 8. Did your partner experience discomfort from the device when you user having sex? (Response: Always, Most of the time, Some of the time, Rarely, Never)
- 9. If Ovaprene® became available and you needed protection from pregnancy, would your partner's discomfort prevent you from using it? (Response: No, Yes)
- 10. Do you think it would be possible for a woman to use this product without her partner's knowledge? (Response: No, Yes)
- 11. While you have already had tubal sterilization, if you needed protection against pregnancy, how likely would you be to use Ovaprene® if it became available? (Response: Very unlikely, Unlikely, Likely, Very likely)
- 12. Have you ever used a diaphragm when you needed protection against pregnancy? (Response: No, Yes)
- 13. While you have already had tubal sterilization, if you needed protection from pregnancy and you could only choose between Ovaprene® and a diaphragm, which would you choose? (Response: Ovaprene®, Diaphragm)
- 14. How likely would you be to recommend Ovaprene® to a friend who needed protection against pregnancy if Ovaprene® became available? (Response: Very unlikely, Unlikely, Likely, Very likely)

There are a few open-ended questions in the questionnaire, such as the following four:

- List up to three things you like about Ovaprene®
- List up to three things you don't like about Ovaprene®
- Do you have any suggestions for changes or improvements to the Ovaprene device? (No, Yes-please describe)
- Please write down any additional comments you have not reported elsewhere on this
  questionnaire and that you would like to share with us.

These open-ended questions will be summarized categorically with all actual responses, after some basic processing, such as removing redundant spaces (i.e., double spaces) between words, converting texts to lower cases, but making the first letter of a sentence in upper case.

Frequencies of answers to the closed-ended acceptability questions will also be cross-tabulated with Ovaprene device position (based on digital exam) after linking the Device Position CRF data with Acceptability Questionnaire CRF data.

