# 14.2.5 Tertiary: Acceptability

Tables and listings will be created for all responses on the acceptability questionnaire/eDiary. Results will be evaluated qualitatively. There are no planned statistical tests for this objective.

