| Tertiary: 4. Acceptability | 
 
a) Response on acceptability questionnaire/diary:         
 
Problems with insertion, including confirmation of placement
 
Aspects liked most and least by the female partner
 
Dislodgements reported by the female partner
 
Comfort reported by both partners during intercourse and whether discomfort, if reported, was bothersome and would keep the person from using the device again
 
 
 
 | Ovaprene® safety cycle & Ovaprene® PCT cycles                                 |
| 5. Fit                     | a) Proportion of subjects who can be fitted with Ovaprene®.   | Baseline PCT cycle  |
|                            | b) Proportion of subjects who can correctly insert, position, and remove the device using written instructions only.  | Baseline PCT
cycle, Ovaprene®
safety cycle &
Ovaprene® PCT
cycles |
|                            | c) Proportion of subjects who require assistance to correctly insert, position, and remove the device.  | Baseline PCT cycle, Ovaprene®   |

|   | safety cycle &
Ovaprene® PCT
cycles |
|---|---|
| 
 
d) Location of Ovaprene® in relation to the cervix as
determined by clinical exam; relationship of position to PCT
results, safety, and acceptability.
 
 | Ovaprene® safety cycle & Ovaprene® PCT    |
|   | cycles                                    |

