#### 4.2.1 Planned Tables

The format of each unique table is provided in a separate document of "Table Shells". Some outputs from statistical programming may be slightly different in layout from that illustrated in "Table Shells". The table shells will not be amended to match the actual tables in such cases.

| Table Number | Table Title   | Population |
|---------------------|---|-------------------|
| 14.1.1              | Summary of Subject Disposition and Reasons for Discontinuation  | All Screened      |
| 14.1.2              | Number and Percent of Subjects at Each Study Visit  | All Enrolled      |
| 14.1.2-E            | Number and Percent of Subjects at Each Visit and Time Point in East Virginia Medical School                 | All Enrolled      |
| 14.1.3-En           | Summary of Subject Disposition by Study Site for All Enrolled Population                                    | All Enrolled      |
| 14.1.3-Ca           | Summary of Subject Disposition by Study Site for Caya Population  | Caya              |
| 14.1.3              | Summary of Subject Disposition by Study Site  | Ovaprene          |
| 14.1.4-Ca           | Summary of Protocol Deviations by Cycle for Caya Population   | Caya              |
| 14.1.4              | Summary of Protocol Deviations by Cycle   | Ovaprene          |
| 14.1.5-En           | Summary of Demographics for All Enrolled Population   | All Enrolled      |
| 14.1.5-Ca           | Summary of Demographics for Caya Population   | Caya              |
| 14.1.5              | Summary of Demographics   | Ovaprene          |
| 14.1.6-En           | Summary of Medical History for All Enrolled Population  | All Enrolled      |
| 14.1.6-Ca           | Summary of Medical History for Caya Population  | Caya              |
| 14.1.6              | Summary of Medical History  | Ovaprene          |
| 14.1.7-En           | Summary of Gynecological History for All Enrolled Population  | All Enrolled      |
| 14.1.7-Ca           | Summary of Gynecological History for Caya Population  | Caya              |
| 14.1.7              | Summary of Gynecological History  | Ovaprene          |
| 14.1.8-En           | Summary of Contraceptive History for All Enrolled Population  | All Enrolled      |
| 14.1.8-Ca           | Summary of Contraceptive History for Caya Population  | Caya              |
| 14.1.8              | Summary of Contraceptive History  | Ovaprene          |

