| 14.2.2.3-NE          | Summary of Cervical Mucus pH Values at Non-EVMS Sites  | Ovaprene with at Least One PCT Cycle |
| 14.2.2.4-E           | Summary of Vaginal Lateral Wall pH Values at Study Site EVMS   | Ovaprene with at Least One PCT Cycle |
| 14.2.2.4-NE          | Summary of Vaginal Lateral Wall pH Values at Non-EVMS Sites  | Ovaprene with at Least One PCT Cycle |
| 14.2.2.5             | Summary of Residual Amount of Ferrous Gluconate in Device  | Ovaprene with at Least One PCT Cycle |
| 14.2.2.5-Dur         | Summary of Residual Amount of Ferrous Gluconate in Device by Duration of Time the Device was Worn  | Ovaprene with at Least One PCT Cycle |
| 14.2.2.6             | Summary of Cervical Mucus Scores by Visit  | Ovaprene with at Least One PCT Cycle |
| 14.2.2.6-Ca          | Summary of Cervical Mucus Scores by Visit for Caya Population  | Caya                                 |
| 14.2.2.7             | Number and Percentage of Subjects with Cervical Mucus Score at Least 10 by Cycle   | Ovaprene with at Least One PCT Cycle |
| 14.2.2.7-Ca          | Number and Percentage of Subjects with Cervical Mucus Score at Least 10 by Cycle for Caya Population   | Caya                                 |
| 14.2.3.1             | Summary of Open-ended Acceptability Questions  | Ovaprene                             |
| 14.2.3.2             | Summary of Closed-ended Acceptability Questions  | Ovaprene                             |

| Table Number | Table Title   | Population |
|--------------|---|-------------------|
| 13.2.3.3     | Summary of Acceptability Questions by Ovaprene Device Position Based on Digital Exam  | Ovaprene          |
| 14.2.4.1A    | Shifts of Acceptability from Visit OS5 to Visit OP3A – Part A   | Ovaprene          |
| 14.2.4.1B    | Shifts of Acceptability from Visit OS5 to Visit OP3A – Part B   | Ovaprene          |
| 14.2.4.1C    | Shifts of Acceptability from Visit OS5 to Visit OP3A – Part C   | Ovaprene          |
| 14.2.4.1D    | Shifts of Acceptability from Visit OS5 to Visit OP3A – Part D   | Ovaprene          |
| 14.2.4.1E    | Shifts of Acceptability from Visit OS5 to Visit OP3A – Part E   | Ovaprene          |
| 14.2.4.2A    | Shifts of Acceptability from Visit OS5 to Visit OP3B – Part A   | Ovaprene          |
| 14.2.4.2B    | Shifts of Acceptability from Visit OS5 to Visit OP3B – Part B   | Ovaprene          |
| 14.2.4.2C    | Shifts of Acceptability from Visit OS5 to Visit OP3B – Part C   | Ovaprene          |

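### SAP 3.8 tabulates open-ended likes and dislikes as cleaned verbatim text, so counts per aspect are fragmented and Table 14.2.3.1 cannot directly show what women liked most and least

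*SAP*

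**What the plan says.** The tertiary acceptability endpoint in SAP 2.4 (and Protocol section 6) is the set of responses on the questionnaire and diary. One of its items is "Aspects liked most and least by the female partner". The questionnaire items that feed it are free text: "List up to three things you like about Ovaprene", with a matching item for dislikes.

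SAP 3.8 states how the free text is handled: "These open-ended questions will be summarized categorically with all actual responses, after some basic processing, such as removing redundant spaces". The other step named is "converting texts to lower cases, but making the first letter of a sentence in upper case". The result goes into Table 14.2.3.1, "Summary of Open-ended Acceptability Questions", for the Ovaprene population. The general convention for discrete variables in SAP 3.1.3 is a count and percentage per category.

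Protocol 14.2.5 sets the wider frame: "Tables and listings will be created for all responses on the acceptability questionnaire/eDiary", and then "Results will be evaluated qualitatively. There are no planned statistical tests for this objective".

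**The concern.** To say what was liked most or least across the study, one needs the number of women who mentioned each aspect. A categorical summary of verbatim text counts something else, namely how many entries are identical after cleaning. Two women who both found insertion easy but said so differently fall in separate rows of one each.

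The plan treats other free text differently. Adverse events are coded to MedDRA (SAP 3.7.1) and medications to WHO Drug (SAP 3.5.6), and each has a rule that a subject is counted once per term or class. The likes and dislikes have no coding frame, no rule for synonyms and no count-once rule. A woman may give three likes and three dislikes on each questionnaire, so it is also unclear whether a percentage would refer to women or to entries.

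At stake is the usefulness of one descriptive tertiary table. If it cannot rank aspects, any grouping will be done after the answers have been seen, in an open-label study.

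**Working it through.** The documents give no count, proportion, test or sample size for this endpoint, so there is no figure of the plan to reproduce. The check has four parts. All example answers, shares and numbers of wordings are assumptions.

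**1. Can the named cleaning steps merge the same idea?** Collapsing double spaces, lower-casing and capitalising the first letter were applied to ten made-up answers, eight about easy insertion and two about the absence of hormones.

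- *Easy to insert*, *easy  to insert* (double space) and *EASY TO INSERT* merged into one row of 3.
- *Insertion was easy*, *It goes in easily*, *simple to put in*, *Easy insertion* and *easy to insert.* (with a full stop) each stayed alone.
- *no hormones* and *Non-hormonal* stayed apart.

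Two themes became 6 + 2 = 8 rows. All ten answers were still shown. Only the count per theme was split.

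**2. How far can the largest row fall?** Suppose m women each name an aspect once, in k different wordings. The largest row is at least ceil(m/k) (an even split) and at most m − k + 1 (one common wording, the rest single). Take n = 25 women, the approximate target for completers in SAP 2.3, and m = 10. The share of women is then 10/25 = 40.0%.

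| Wordings k | Largest row, lowest to highest | Percent of 25 women |
|---|---|---|
| 1 | 10 | 40.0% |
| 2 | 5 to 9 | 20.0% to 36.0% |
| 4 | 3 to 7 | 12.0% to 28.0% |
| 8 | 2 to 3 | 8.0% to 12.0% |
| 10 | 1 | 4.0% |

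With 45 women, the approximate recruitment ceiling, and the same 40.0% share (18 women), the largest row runs from 18 (40.0%) to 1 (2.2%).

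The order of aspects can also reverse. An aspect named by 10 women and spread evenly over 4 wordings has a largest row of 3. An aspect named by 5 women in identical words has a row of 5 and would stand above it.

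**3. Women or responses?** With 25 women there are up to 25 × 3 = 75 likes and 75 dislikes per visit. The schedule in SAP 4.1 administers the questionnaire at OS5, OP3A and OP3B, so the maximum is (75 + 75) × 3 = 450 entries. If every slot is filled, an aspect named by 10 women at one visit is 10/25 = 40.0% of women but 10/75 = 13.3% of like entries. SAP 3.1.3 sets the denominator as the non-missing observations or else the population size. For an item with several entries per woman, this does not settle which is meant.

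**4. Which aspects depend on the free text?**

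- Closed questions in SAP 3.8 cover ease of insertion (question 1), awareness in daily activities (2), comfort without and during sex (3 and 5), and partner awareness and discomfort (7 and 8).
- Clinicians record whether the woman can remove the device (SAP 3.9 d).
- Dislodgement is captured in the diary and by clinician examination (SAP 3.9 g and h) and is a subgroup of the primary analysis (SAP 3.6).
- None of the 14 closed questions asks what was liked or disliked. Possible themes such as being hormone-free, monthly use, and discharge or odour have no closed acceptability question.

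**The case against.** The strongest reply is that the plan does what the protocol asks. Protocol 14.2.5 wants all responses tabulated and listed and then judged qualitatively. No proportion or ranking of aspects is defined, and the items ask each woman for a list, not an order. With about 25 completers, a reader can group the answers by hand, and verbatim display avoids coder judgement. The cleaning steps are introduced as examples, and the table layouts are in a separate document of shells that was not available. Most of the obvious themes are measured elsewhere.

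Much of this stands, and it rules out three stronger readings that a reader might infer.

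- *The endpoint is undercounted.* The documents do not support this. No aspect-level count is defined as the endpoint, and no response is dropped.
- *Only spaces and case will be cleaned.* The text does not say so, because the list is illustrative.
- *A common problem such as the device slipping would be hidden.* It would not, since diary and clinician data capture it independently.

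What does not stand is that the table is adequate as planned. The SAP chose a categorical summary, and nothing in its wording points to grouping by theme. SAP 4.2.1 describes the shells as table formats, so a coding rule belongs in the SAP text. Qualitative evaluation is a reason to group transparently and in advance. SAP 1.0 lets departures that are not significantly different be described in the study report without amendment, so grouping could be added later, but then by someone who has seen the answers.

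**Conclusion.** The point holds as a limited one. The planned table would fragment counts per aspect, could not directly show which aspects were liked most and least, and leaves open whether percentages refer to women or to responses. The loss depends on how women phrase their answers and cannot be calculated from the documents. In the illustration the largest row for an aspect named by 10 of 25 women lies anywhere from 10/25 (no loss) to 1/25, and no single value in that range can be defended as the expected one. This rests on reading SAP 3.8 together with SAP 3.1.3, and on the unseen table shells containing no coding rule. The consequence is confined to a descriptive tertiary output and is greatest for aspects without closed-question, diary or clinician data. No primary or safety conclusion is affected. It is a worthwhile improvement, not a defect that threatens the study.

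**What to change.** In SAP 3.8, add that the like and dislike responses will be coded before tabulation to a short theme list with an 'other' category, fixed before database lock. The list could include insertion, removal, comfort, awareness in daily life, dislodgement, partner awareness or discomfort, hormone-free, monthly use, and discharge or odour.

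In Table 14.2.3.1, report the number and percent of women naming each theme at OS5, OP3A and OP3B, counting each woman once per theme per visit, and state the denominator. Keep the verbatim text in a listing. SAP 4.2.2 already commits to listing all collected data.

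The cost is a short addition to the SAP and a few hours of existing staff time. The downside is a small element of judgement in assigning themes. A second independent coder would limit it, and the listing lets a reader check the coding.
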